### 5.1.2 Justification of the Study Design

QHD04 study will describe the safety of the 3 different dosages of QIV-HD in children 6 months to 17 years of age. The study will also describe the immunogenicity of the different dosages of QIV-HD compared to a unadjuvanted QIV-SD (Fluarix Quadrivalent, licensed in the US) in all stages of the study and compared to an adjuvanted TIV (FLUAD Pediatric, licensed in Canada) during Stage 4 after the highest acceptable dosage of QIV-HD is established. Both comparators will be obtained commercially and will be used according to the approved indication.

Given the different volumes in the 3 different dosages of the QIV-HD and the comparator vaccines, QHD04 will be a staged, modified double-blind study with an unblinded administrator used at each study site. The administrator will not be involved in any of the blinded study assessments (eg, safety).

Since this is the first time that the QIV-HD will be administered to the pediatric population, an ESDR will be performed for subjects 6 months to 8 years of age prior to dosage ascension (30, 45, and 60 µg HA/strain/dose).

Given the matured immune system in children 9 to 17 years of age, no ESDR will occur for subjects 9 to 17 years of age prior to dosage ascension. Subjects 9 to 17 years of age will be randomized to receive the 30 and 45 µg HA/strain/dose vaccines separately from subjects 9 to 17 years of age who receive the 60 µg HA/strain/dose formulation in order to maintain the randomization ratio across all age groups and thus allow for pooling of the 30, 45, and 60 µg HA/strain/dose formulations across all age groups as well.

The comparison of the QIV-HD that will be used in Stage 4 (highest dosage with acceptable safety) to the adjuvanted TIV will be an indicator in terms of expected vaccine efficacy since FLUAD Pediatric is the only licensed pediatric vaccine with studies evaluating both HAI immunogenicity and relative efficacy data.

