**Active substances:**

- A/Singapore/GP1908/2015 IVR-180 (H1N1)  
(A/Michigan/45/2015 [H1N1] pdm09-like virus) 7.5 µg HA
- A/Singapore/INFIMH-16-0019/2016, IVR-186 (H3N2) 7.5 µg HA
- B/Maryland/15/2016 (B/Colorado/06/2017-like virus, Victoria lineage) 7.5 µg HA

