5.1 Statistical Methods

5.1.1 Hypotheses and Statistical Methods for the Objectives

5.1.1.1 Hypotheses

No hypotheses for safety and immunogenicity are planned. All analyses are descriptive.

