5.1.1.2 Statistical Methods

For the cohorts controlled by the non-adjuvanted QIV-SD, results will be described per stage, according to vaccine received, per age group. Age groups will also be pooled within the same vaccine group for the main endpoints. When age groups are pooled, since age distributions between QIV-HD groups and the pooled QIV-SD group are different, the Simpson Paradox might exist. Therefore, each QIV-HD group (30 μ g, 45 μ g, and 60 μ g) will be compared with its corresponding and restricted QIV-SD group (ie, QIV-SD control group restricted to relevant study groups for comparison to QIV-HD at 30 μ g, QIV-HD at 45 μ g, and QIV-HD at 60 μ g respectively) to reduce the potential bias. If any of the stages are not completed, analyses for the higher dose or next stage will not be performed.

For the cohort controlled by the adjuvanted TIV, results will be described according to vaccine received.

For main safety analyses, results will be described based on both “after any vaccination” and “after each vaccination”.

For main immunogenicity analyses, results will be described based on both “after last vaccination” and “after each vaccination”. Subgroup immunogenicity analyses per previous vaccination status and/or baseline serostatus may be presented when appropriate. Comparison between each QIV-HD group (30 μ g, 45 μ g, and 60 μ g) and the pooled QIV-SD group will also be performed stratified on age groups for immunogenicity endpoints.

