where $\alpha_i = \delta_i \sum_{k=1}^s V_k^{-1} - \sum_{k=1}^s \delta_k V_k^{-1}$, $\beta_i = V_i^{-1} \left(1 + \alpha_i \sum_{k=1}^s f_k \delta_k \right)$, $V_i = V(\hat{\delta}_i)$, and f_i is the fraction of subjects in the target population that belong in stratum i ($\sum_{i=1}^s f_i = 1$).

In addition, a sensitivity analysis will be performed with adjustment on the baseline titers. When comparing the GMT ratio between each QIV-HD group (30 μ g, 45 μ g, and 60 μ g) and the pooled QIV-SD group, the 95% CI will be stratified on both age effect and baseline titers and calculated using General Linear Model (GLM). When comparing the GMT ratio between each QIV-HD group and the QIV-SD group per age group, an ANCOVA model will be used when considering the baseline titer as a covariate. Results will be presented in Appendix 15 of the CSR.

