5.5 Determination of Sample Size and Power Calculation

QHD04 is a Phase II study to describe the safety and immunogenicity of 3 different dosages of QIV-HD. The sample size is not powered. The study will include a total of approximately 700 subjects that will be divided into 13 groups as follows:

- Groups 1, 2, 3, 5, 9, and 10 will each include 40 subjects (previously influenza vaccinated or previously influenza unvaccinated) in a 3:1 ratio (QIV-HD: QIV-SD).
- Group 4 will include 90 subjects (previously influenza vaccinated or previously influenza unvaccinated) in a 1:1 ratio (QIV-HD: QIV-SD).
- Groups 7 will include 60 subjects who are previously influenza vaccinated in a 1:1 ratio (QIV-HD: QIV-SD).
- Groups 6 and 8 will each include 60 subjects who are previously influenza unvaccinated in a 1:1 ratio (QIV-HD: QIV-SD or TIV).
- Group 11 and 13 will each include 60 subjects (previously influenza vaccinated or previously influenza unvaccinated) in a 1:1 ratio (QIV-HD: QIV-SD).
- Group 12 will include 70 subjects (previously influenza vaccinated or previously influenza unvaccinated) in a 3:3:1 ratio (QIV-HD: QIV-HD: QIV-SD).

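### The baseline-titre-adjusted sensitivity analysis covers only QIV-HD versus QIV-SD and should be extended to QIV-HD versus adjuvanted TIV in Group 8

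*SAP*

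**What the plan says.** The last paragraph of SAP 5.1.1.2.2 adds a sensitivity analysis adjusted for baseline titre, to be reported in Appendix 15 of the clinical study report. It has two parts, and both name QIV-SD as the comparator. One is a general linear model with age and baseline titre for each QIV-HD dosage against pooled QIV-SD. The other is by age group: "When comparing the GMT ratio between each QIV-HD group and the QIV-SD group per age group, an ANCOVA model will be used", with baseline titre as the covariate.

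For the adjuvanted TIV cohort, SAP 5.1.1.2 has one sentence: "For the cohort controlled by the adjuvanted TIV, results will be described according to vaccine received". It gives no model, covariate or strain list. The GMT ratio in Group 8 therefore falls under the general method of SAP 5.1.1.2.2, an unadjusted two-sample t interval on log10 titre with pooled variance.

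D0 titres are available in this cohort: SAP 4.4.2.1 lists D0, D28 and D56 titres for previously unvaccinated children aged 6 months to 8 years. On size, SAP 5.5 says "Groups 6 and 8 will each include 60 subjects who are previously influenza unvaccinated in a 1:1 ratio" and "The sample size is not powered". On purpose, Protocol 5.1.2 says the comparison with adjuvanted TIV "will be an indicator in terms of expected vaccine efficacy".

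On composition, Protocol 6.1.5.1 lists one H1N1, one H3N2 and one B/Victoria strain for adjuvanted TIV. Protocol 6.1.1.1, 6.1.2.1 and 6.1.3.1 show that every QIV-HD dosage also contains B/Phuket/3073/2013 (Yamagata).

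**The concern.** The comparison with adjuvanted TIV is the only one that the protocol links to expected efficacy, and it has just 30 children per arm. It is also the one immunogenicity comparison left out of the baseline-adjusted analysis, and the SAP gives no reason.

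Some baseline spread is plausible in children of 6 to < 24 months. Protocol 5.2.5 excludes earlier laboratory-confirmed influenza, and the Visit 1 procedures in Protocol 5.1.4 check for a known diagnosis, but unrecognised infection can remain. Stage 4 is planned for January and February 2019 (Protocol 5.1.5), within the 2018-2019 season. Maternal antibody is another possible source.

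At stake are some precision and a check on whether a chance difference in D0 titres explains part of the observed ratio. If that check is added only after the D28/D56 data are unblinded, it will not be prespecified.

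**Working it through.** **Sizes in the plan.** The groups in SAP 5.5 sum to 6×40 + 90 + 60 + 2×60 + 2×60 + 70 = 700, as stated. Group 8 is 60 at 1:1, so 30 per arm. The plan states no precision figure.

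**Assumed inputs.** The documents give neither the SD of log10 titre nor the baseline/post correlation r. I take SD 0.4 to 0.7 and r 0.1 to 0.7.

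**Planned interval.** The half-width on log10 is t(0.975, 58) × SD × √(1/30 + 1/30). At SD 0.6 this is 2.002 × 0.6 × 0.2582 = 0.310, so the ratio is multiplied or divided by 10^0.310 = 2.04. At SD 0.4, 0.5 and 0.7 the factor is 1.61, 1.81 and 2.30.

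**With baseline as covariate.** The half-width is t(0.975, 57) × SD × √(1 − r²) × √(2/30) × √(1 + 1/56). The last term allows for average chance imbalance in the covariate.

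| r | CI factor at SD 0.6 (unadjusted 2.04) | Change in log-scale width | Equivalent n per arm, 30/(1 − r²) |
|---|---|---|---|
| 0.1 | 2.05 | 0.4% wider | 30.3 |
| 0.2 | 2.03 | 1.1% narrower | 31 |
| 0.3 | 1.99 | 3.7% narrower | 33 |
| 0.5 | 1.87 | 12.6% narrower | 40 |
| 0.7 | 1.67 | 27.9% narrower | 59 |

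The percentage change does not depend on the SD. The last column ignores the small degrees-of-freedom and imbalance costs.

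**Many titres below 10 at D0.** SAP 4.4.2.1 sets these to LLOQ/2 = 5, which compresses the baseline. I simulated 30 per arm with residual SD 0.5, seropositive children at 10 to 80 and all others at 5. With 5% to 10% seropositive, adjustment narrows the interval by 0.7% to 2.0% (slope 0.5) or 5% to 10% (slope 1.0). With 30% seropositive, the gain is 6% or 21%.

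**Chance imbalance.** With baseline log10 SD 0.5, the 95% range of the chance baseline ratio reaches 10^(1.96 × 0.5 × 0.2582) = 1.79-fold. The share carried into the post-vaccination ratio is set by the slope, r × 0.6/0.5:

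- r = 0.3: slope 0.36, 1.79^0.36 = 1.23-fold
- r = 0.5: slope 0.60, 1.79^0.60 = 1.42-fold
- r = 0.7: slope 0.84, 1.79^0.84 = 1.63-fold

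If only 10% had a D0 titre of 40 and the rest 5, the baseline SD would be log10(8) × √(0.1 × 0.9) = 0.27. The chance ratio would then reach 10^(1.96 × 0.27 × 0.2582) = 1.37-fold.

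**Strains.** Reverse cumulative curves are planned for each strain (SAP 5.1.1.2.2), and SAP 4.4.2.1 provides titres for each strain. No text sets a different scope for the TIV cohort. A B/Yamagata ratio is therefore neither excluded nor specifically planned.

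**The case against.** Four arguments go the other way.

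- **Only a sensitivity analysis is missing.** The main QIV-SD ratios are not baseline-adjusted either, so Group 8 gets the same main method as the unstratified QIV-SD comparisons. This stands, and adding the analysis leaves the main Group 8 interval unchanged.
- **This may be the cohort where adjustment helps least.** These children have had no influenza vaccine and no laboratory-confirmed influenza. This also stands: the gain is under 4% at a correlation of 0.3 or less.
- **Baseline already enters other outputs.** D28/D0 and D56/D0 ratios, seroconversion and baseline curves would show an imbalance. That is true, but individual ratios fix the slope at 1, and between-group contrasts are specified only for GMTs and seroconversion rates. Serostatus subgroups and additional parameters are optional.
- **The trial is descriptive.** The SAP says "No hypotheses for safety and immunogenicity are planned. All analyses are descriptive", so there is no success rule. This limits the consequence but does not explain why one objective lacks an analysis that the other two have.

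A reader might infer three stronger things that the documents do not support:

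- **That the planned interval is needlessly imprecise.** Its width comes mainly from 30 per arm, and the documents give neither the correlation nor D0 seropositivity.
- **That a baseline imbalance passes in full into the GMT ratio.** It carries over only in proportion to the slope. Under randomisation it is chance variation that the planned interval already covers, not bias.
- **That the plan means to infer efficacy from B/Yamagata.** No text says so. The SAP is silent, each strain is analysed separately, and the output shells are deferred to the full tables, listings and figures.

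**Conclusion.** The gap is real and modest. The baseline-adjusted sensitivity analysis omits the comparison with adjuvanted TIV although the D0 titres exist and this comparison carries the efficacy-related interpretation. The benefit runs from nothing (correlation near 0.1) through about 4% (0.3) and 13% (0.5) to 28% (0.7) in log-scale interval width. It also removes whatever part of a chance baseline imbalance carries over. All these sizes rest on assumed SDs and correlations.

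The strain point is secondary and concerns interpretation, not precision. A B/Yamagata ratio compares a vaccine containing the antigen with one lacking it, so it cannot inform an efficacy reading based on adjuvanted TIV.

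**What to change.** In SAP 5.1.1.2.2, extend the sensitivity ANCOVA with log10 baseline titre to Group 8 QIV-HD versus adjuvanted TIV, at D28 and D56, for HAI and SN. Add one sentence saying that the efficacy-related comparison rests on H1N1, H3N2 and B/Victoria, and that B/Yamagata is shown separately as descriptive because adjuvanted TIV does not contain it.

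The cost is two SAP sentences and one extra set of model outputs. The adjusted model also needs a D0 titre, whereas the immunogenicity analysis set requires only a post-vaccination sample, and Protocol 5.1.4 allows vaccination after a failed baseline draw. Any such child drops out of the adjusted model, so its n should be shown beside the unadjusted n. As an illustration at SD 0.6, 27 per arm adjusted gives a factor of 2.07 at r = 0.3 and 1.94 at r = 0.5, against 2.04 for 30 per arm unadjusted.

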5.2 Analysis Sets

Two main analysis sets will be used: IAS and SafAS

5.2.1 Immunogenicity Analysis Set

The IAS is defined as the subset of randomized subjects who received 1 dose of a study vaccine (for subjects 9 to 17 years of age and for previously influenza vaccinated subjects 6 months to 8 years of age) or 2 doses of a same study vaccine (for previously influenza unvaccinated subjects 6 months to 8 years of age) and had a post-vaccination blood sample. Subjects will be analyzed as treated.

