#### 5.2.7.2 Definitive Contraindications

The following criteria are applicable to subjects who had never received any influenza vaccine before the start of the study and who will be receiving 2 influenza vaccine injections during the study (1 at V01 and 1 at V03). Should a subject experience 1 of the conditions listed below, the Investigator will discontinue vaccination.

- D01: An anaphylactic or other significant allergic reaction to the previous dose of vaccine
- D02: Receipt of any immune globulins, blood, or blood-derived products between V01 and V03.
- D03: Known or suspected congenital or acquired immunodeficiency; or receipt of immunosuppressive therapy, such as anti-cancer chemotherapy or radiation therapy, since the preceding visit; or long-term systemic corticosteroid therapy (prednisone or equivalent for more than 2 consecutive weeks since the preceding visit).
- D04: Thrombocytopenia or bleeding disorder, which may be a contraindication for IM vaccination, based on Investigator's judgement.
- D05: Chronic illness that, in the opinion of the investigator, is at a stage where it might interfere with study conduct or completion.
- D06: Development of any condition that in the opinion of the Investigator would pose a health risk to the subject or could interfere with the evaluation of the study vaccine (including GBS, clinically significant developmental delay, neurologic disorder, seizure disorder, hepatitis B, or hepatitis C).
- D07: Any SAE related to the study vaccines following the previous study vaccination, based on investigator's judgement.

Subjects with a definitive contraindication will not be vaccinated at V03, but will continue to be followed up for the study-defined safety and immunogenicity assessments, as applicable.

In the event of a local or national immunization program with a pandemic influenza vaccine or other vaccine, subjects who receive pandemic influenza vaccine or other vaccine at any time during the study will not be withdrawn from the study.

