3.2 Study Plan

The study plan is summarized in the Table of Study Procedures ([Table 3.2](#), [Table 3.3](#), and [Table 3.4](#)).

Vaccination

All eligible subjects will be randomized to receive 1 or 2 doses of either QIV-HD, Fluarix® Quadrivalent (unadjuvanted QIV-SD), or FLUAD Pediatric® (adjuvanted TIV). The dosage of QIV-HD that is administered will depend on both the age of the subject and the stage at which he / she is enrolled.

- Subjects 9 to 17 years of age will receive 1 dose of the QIV-HD or the comparator vaccine on D0.
- Previously influenza vaccinated subjects 6 months to 8 years of age will receive 1 dose of the QIV-HD or the comparator vaccine on D0.
- Previously influenza unvaccinated subjects 6 months to 8 years of age will receive 2 doses of the QIV-HD or the comparator vaccine. Each dose will be administered 28 days apart (at D0 and D28).

Of note, the highest dosage with an acceptable safety review in prior stages will determine the dose evaluated in Stage 4.

An unblinded administrator at each site will administer the vaccine.

Blood Sampling

Subjects will provide 2 or 3 blood samples, regardless of the stage of enrollment:

- Subjects 9 to 17 years of age will provide a pre-vaccination (baseline) blood sample at V01 (D0) and a post-vaccination blood sample at V03 (D28 [+7 days]) for HAI and SN testing.
Note: Subjects 9 to 17 years of age are scheduled for 2 site visits. However, the second visit is designated as V03 to be consistent with the visits nomenclature of the 6 months to 8 years age groups.
- Previously influenza vaccinated subjects 6 months to 8 years of age will provide a pre-vaccination (baseline) blood sample at V01 (D0) and a post-vaccination blood sample at V03 (D28 [+7 days]) for HAI and SN testing.
- Previously influenza unvaccinated subjects 6 months to 8 years of age will provide a pre-vaccination (baseline) blood sample at V01 (D0) and a post-vaccination blood sample at V03 (D28 [+7 days]) and V05 (28 days after V03 [+7 days]) for HAI and SN testing.

Note: The blood sample will be taken prior to vaccination during any visit when a subject receives a vaccination.

Collection of Safety Data

All subjects will be observed for 30 minutes after vaccination, and any unsolicited systemic adverse events (AEs) occurring during that time will be recorded as immediate unsolicited systemic AEs in the case report book (CRB).

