4.4.2 Immunogenicity

4.4.2.1 Computed Values for Analysis

The endpoints for the evaluation of immunogenicity by HAI method are:

For subjects 9 to 17 years of age and previously influenza vaccinated subjects 6 months to 8 years of age:

- HAI antibody (Ab) titers obtained on D0 and D28
- Individual HAI titers ratio D28/D0
- Seroconversion (titer < 10 [1/dil] at D0 and post-injection titer ≥ 40 [1/dil] at D28, or titer ≥ 10 [1/dil] at D0 and a ≥ 4-fold increase in titer [1/dil] at D28)
- Percentage of subjects with titers ≥ 40 (1/dil) at D0 and D28

For previously influenza unvaccinated subjects 6 months to 8 years of age:

- HAI Ab titers obtained on D0, D28, and D56
- Individual HAI titers ratio D28/D0 and D56/D0
- Seroconversion (titer < 10 [1/dil] at D0 and post-injection titer ≥ 40 [1/dil] at D28 and D56, or titer ≥ 10 [1/dil] at D0 and a ≥ 4-fold increase in titer [1/dil] at D28 and D56)
- Percentage of subjects with titers ≥ 40 (1/dil) at D0, D28, and D56

The endpoints for the evaluation of immunogenicity by virus SN method are:

For subjects 9 to 17 years of age and previously influenza vaccinated subjects 6 months to 8 years of age:

- Individual neutralization test (NT) Ab titer on D0 and D28
- Individual NT Ab titer ratio (fold increase in serum NT post-vaccination relative to D0) at D28
- Subjects with NT Ab titers ≥ 20 (1/dil), ≥ 40 (1/dil), ≥ 80 (1/dil) at D28
- Fold-increase in NT Ab titer [post/pre] ≥ 2 and ≥ 4 at D28
- Detectable NT (NT Ab titer ≥ 10 [1/dil]) at D0 and D28

For previously influenza unvaccinated subjects 6 months to 8 years of age:

- Individual NT Ab titer on D0, D28, and D56
- Individual NT Ab titer ratio (fold increase in serum NT post-vaccination relative to D0) at D28 and D56
- Subjects with NT Ab titers ≥ 20 (1/dil), ≥ 40 (1/dil), ≥ 80 (1/dil) at D28 and D56
- Fold-increase in NT Ab titer [post/pre] ≥ 2 and ≥ 4 at D28 and D56
- Detectable NT (NT Ab titer ≥ 10 [1/dil]) at D0, D28, and D56

For HAI and SN assays, in order to appropriately manage extreme values (<lower limit of quantification [LLOQ] and \geq upper limit of quantification [ULOQ]) for analysis purposes, the following computational rule is applied to the values provided in the clinical database for each blood sample (BL) drawn:

- If a value is < LLOQ, then use the computed value LLOQ/2
- If a value is \geq LLOQ and < ULOQ (or \leq ULOQ), then use the value
- If a value is \geq ULOQ (or $>$ ULOQ), then use the computed value ULOQ

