5.2.3 Populations Used in Analyses

All randomized subjects with data in the CRB will be taken into account in the description of the population (eg, the disposition, the demographic, or baseline characteristics).

The safety analyses will be performed on the SafAS.

The immunogenicity analyses from HAI assay and SN assay will both be performed on the IAS.

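### The after-dose-1 (D28) immunogenicity results in previously unvaccinated children are limited to those who went on to a matching second dose

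*SAP*

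**What the plan says.** **Analysis set.** SAP 5.2 states: "Two main analysis sets will be used: IAS and SafAS". Neither document defines a further immunogenicity set. For children on the two-dose schedule, SAP 5.2.1 admits those who received "2 doses of a same study vaccine (for previously influenza unvaccinated subjects 6 months to 8 years of age" and who have a blood sample after vaccination; the sample is not tied to a visit. Protocol 12.2.1 has the same rule. SAP 5.2.3 adds: "The immunogenicity analyses from HAI assay and SN assay will both be performed on the IAS".

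**Planned results.** SAP 5.1.1.2 says: "For main immunogenicity analyses, results will be described based on both" the last vaccination and each vaccination. For previously unvaccinated children, SAP 4.4.2.1 lists "HAI Ab titers obtained on D0, D28, and D56", with the D28/D0 ratio and the other HAI and SN endpoints at D28 as well as D56.

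**Order of events at V03.** SAP 3.2 states: "The blood sample will be taken prior to vaccination during any visit when a subject receives a vaccination". Protocol 5.1.4 puts the V03 steps for these children in this order: review of contraindications, blood draw, vaccination.

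**Children not given dose 2.** Under Protocol 5.2.7.2, a child with a definitive contraindication receives no vaccine at V03 but "will continue to be followed up for the study-defined safety and immunogenicity assessments, as applicable".

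**Safety, for contrast.** SAP 5.2.2 works dose by dose, using the vaccine received at the dose in question.

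**The concern.** The D28 result in a two-dose child measures the response to the first dose. Under the present set, whether that result counts depends on what is given after the sample is drawn. Three kinds of sampled child are dropped: those refused dose 2 by the family, those with a definitive contraindication, and those given a different vaccine at dose 2.

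Two things are at stake.

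- **Selection.** Contraindications D01 (significant allergic reaction to the first dose) and D07 (related SAE after the first dose) can depend on which vaccine and dosage the child received. The D28 comparison is then made among children selected after randomization, possibly differently by arm, in a study whose stated goal (Protocol 1.4) is to choose a dosage for Phase III.
- **Unequal treatment of like cases.** The contraindication rules in Protocol 5.2.7 apply only to two-dose children. A one-dose child with a related SAE or a blood product before V03 stays in the set at D28; a two-dose child with the same event does not. If results are shown by previous vaccination status, as SAP 5.1.1.2 allows, the D28 columns would come from differently selected children.

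**Working it through.** **1. Group sizes.** From SAP 5.5: 6×40 + 90 + 60 + 2×60 + 2×60 + 70 = 700, as stated. The documents give no expected size for the immunogenicity set, no dropout rate and no power figure.

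**2. Who is exposed to the rule.**
- Two-dose children only: Groups 6 and 8, 2×60 = 120.
- Mixed Groups 1–5 and 9–11: 4×40 + 90 (Groups 1–5), plus 2×40 + 60 (Groups 9–11) = 390. The two-dose share is not stated.
- Unaffected: Groups 7, 12 and 13, 60 + 70 + 60 = 190.

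So between 120 and 510 children are on the two-dose schedule.

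**3. The relevant rate.** The D28 sample and dose 2 belong to the same visit. A child who leaves before V03 has no D28 sample under any definition. The rate that matters, m, is the proportion sampled at V03 without a matching second dose. The documents do not give it; I assume 1% to 5%.

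| m (assumed) | Expected loss in an arm of 30 (30m) | Chance of losing at least one, 1−(1−m)^30 | Study total, 120m to 510m |
|---|---|---|---|
| 1% | 0.3 | 26% | 1.2 to 5.1 |
| 2% | 0.6 | 45% | 2.4 to 10.2 |
| 5% | 1.5 | 79% | 6 to 25.5 |

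The arm figures apply directly to Groups 6 and 8. In a QIV-SD arm of 10 in the mixed groups fewer children are exposed, but each one lost is 10% of the arm.

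**4. Precision.** SAP 5.1.1.2.2 gives the interval for a GMT ratio as the difference in mean log10 titer ± t × S × √(1/n₁ + 1/n₂). The multiplicative half-width is 10 raised to that margin. With S assumed:

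| S (log10, assumed) | 30 v 30 | 5% lost, 28.5 v 28.5 |
|---|---|---|
| 0.4 | 1.61 | 1.63 |
| 0.6 | 2.04 | 2.08 |

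**5. Selection.** If a fraction d of one arm is dropped and differs from those kept by a gap g, the arm mean moves by d×g.
- Seroconversion, d = 5%, g = 20 points: 0.05×20 = 1 point.
- GMT, d = 5%, g = 0.3 to 0.5 log10: 10^(0.05×0.3) = 1.035 to 10^(0.05×0.5) = 1.059.

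Both gaps are assumptions. The sign depends on whether the dropped children respond better or worse, which the documents do not say.

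**The case against.** The strongest defence is that one completer set keeps the D28 and D56 results on the same eligible children, so the step from first to second dose can be read directly. The study is descriptive and unpowered, and step 4 shows that the intervals barely move. Attrition related to dosage would also be visible elsewhere: safety is analysed dose by dose, and disposition covers all randomized subjects with data. The protocol promises continued immunogenicity follow-up only where applicable, which is not a promise of inclusion in the set. All of this stands as to size. It does not explain why a first-dose result should be conditional on the second dose, and a completer table can still be shown alongside.

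Four stronger readings are tempting and should not be adopted.

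- *Every exclusion turns on something that happened after the draw.* This holds for receipt of dose 2 itself, for refusal after sampling and for a wrong second vaccine. Contraindications are reviewed before the blood draw at V03, so there the reason precedes the sample.
- *Every discarded D28 titer is sound.* D02 (immune globulins or blood products) and D03 (immunodeficiency, immunosuppression, prolonged corticosteroids) can alter the titer. Protocol 6.7 itself classes such products as affecting the immune response.
- *Each dose-2 non-completer costs a D28 result.* A general dropout rate of 3% to 10% applied to 30 children would give 0.9 to 3 lost and a 60% to 96% chance of losing at least one. But children who miss V03 have no D28 sample to lose, so that calculation answers a different question.
- *The rule favours the higher dosages.* The documents give no rates of D01 or D07 by dosage and no link between tolerability and titer. Selection is possible; its direction is unknown.

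**Conclusion.** The point holds in a limited form. For previously unvaccinated children aged 6 months to 8 years, the only immunogenicity set makes the planned D28 results depend on a matching second dose given after the D28 sample. No other defined set recovers the excluded samples, and one-dose children with the same intervening events are not excluded.

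The effect is probably small: 0.3 to 1.5 children in an arm of 30 if 1% to 5% are sampled at V03 without a matching second dose, with almost no change in interval width. The reason to act is possible vaccine-dependent selection, together with inconsistent handling of one-dose and two-dose children. Results after the last vaccination in two-dose children are not touched by this objection. All loss rates, standard deviations and gaps above are assumptions, because the documents supply none.

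**What to change.** Define the immunogenicity set by time point in SAP 5.2.1 and Protocol 12.2.1.

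- **D28 results:** randomized subjects who received dose 1 and have a D28 sample, analysed by the vaccine received at dose 1.
- **D56 and after-last-vaccination results in two-dose children:** two doses of the same vaccine and a D56 sample.
- **Reporting:** give the number excluded at each time point, by arm and reason.
- **Flag:** mark children with D02 or D03 events, because their D28 titers may be affected, so that the D28 tables can be repeated without them. The concomitant-medication record to D28 (Protocol 6.7) allows treatment exposures of the same kind to be flagged in one-dose children.

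The cost is a change of wording in both documents, one more analysis-set flag and a short exclusion table. No new data are needed. The downside is that D28 and D56 denominators may differ slightly; a D28 table in two-dose completers can be kept as supportive output for anyone who wants the two time points on the same children.
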